9 STATISTICAL ANALYSIS

Analysis Sets

Safety Population: The safety population will include all enrolled subjects who received the treatment.

Efficacy Population: The efficacy population will include all enrolled subjects who received the treatment as specified in the protocol and met all eligibility criteria.

The primary safety endpoint is the proportion of subjects without any localized or systemic safety event through 30 days that affect the venous access circuit and resulted in surgery, hospitalization, or death. Safety events in this calculation will not include venous outflow obstructions which are captured in the calculation of assisted primary patency of the target lesion, assisted primary patency of the venous outflow circuit, and index of patency function. This is an observational study, and outcomes will be summarized, but no comparisons will be performed. Confidence intervals will be provided for all outcome calculations wherever possible.

The primary effectiveness endpoint is the proportion of subjects with target lesion Primary Patency at 30 days. Time to loss of target lesion Primary Patency is defined as the time interval of uninterrupted patency from initial study procedure to the next intervention performed on the target lesion or uncorrectable target lesion occlusion, whichever occurs first.

Sample Size

A sample size of approximately 50 subjects was chosen as appropriate for an initial safety and efficacy evaluation.

The primary effectiveness analyses of target lesion Primary Patency at 30 days will be summarized using number and proportion of subjects with Target Lesion Primary Patency at that timepoint.

This methodology will be repeated to test secondary endpoints, proportion of subjects with: target lesion Primary Patency at 3, 6, and 12 months; Assisted Primary Patency of target lesion at 3, 6, and 12 months; Primary Patency of the venous outflow circuit at 3, 6, and 12 months; Assisted Primary Patency of the venous outflow circuit at 3, 6, and 12 months.

The primary safety endpoint will be summarized using number and proportion of subjects without any localized or systemic safety event that affected the access or venous outflow circuit and resulted in surgery or hospitalization or death through 30 days.

A formal interim analysis will be completed when all subjects complete the 6-month visit, (Visit 4), (or discontinue prior to the 6-month visit). As the interim analysis will be the primary effectiveness analysis, no alpha adjustment for multiplicity will be applied for this interim analysis. The final analysis will be completed when all subjects complete the study (12-month visit; Visit 5).

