3.2 Exclusion Criteria

1. Subject has undergone a surgical intervention of the AVF/AVG ≤ 30 days from the date of the initial study procedure
2. Subject has had a previous stent or stent graft placed in the venous outflow circuit ≤ 30 days from the date of the initial study procedure
3. Active hemodialysis access is not in the arm
4. A pseudoaneurysm is present within the target lesion
5. Target lesion is:
 - a. in the superior vena cava
 - b. in the jugular vein
 - c. under the clavicle
 - d. requires stent graft placement across the elbow
 - e. in the needling segment of an AVF or AVG anastomosis
 - f. located within a stent
6. Lesions, other than the target lesion, in the venous outflow circuit with $>30\%$ stenosis
 - a. Note that subjects with secondary lesions may be included IF the lesions have been treated > 30 days before study procedure AND have less than 30% residual stenosis

7. Known or suspected infection of the hemodialysis access site and/or septicemia
8. Permanent pacemaker or automated implantable cardioverter defibrillator (AICD) on the side with the target lesion
9. Current central venous catheter for dialysis access
10. Uncorrectable coagulation disorders
11. Hypersensitivity to nickel titanium alloy
12. The subject is enrolled in another investigational study
13. The subject is unable or unwilling to comply with the protocol requirements
14. Life expectancy is ≤ 12 months
15. Subject cannot receive heparin or equivalent anticoagulant
16. Allergy to radiographic contrast material which cannot be adequately premedicated
17. Subject is pregnant, breastfeeding, or pre-menopausal and intending to become pregnant
18. Subject's access is anticipated to be abandoned within 3 months
19. Subject has a thoracic central vein obstruction that would lead to stent graft placement across the internal jugular vein
20. Subject's hemodialysis access is thrombosed
21. Active malignancy other than non-melanomatous skin cancer
22. Any other condition deemed exclusionary in the opinion of the investigator

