6 SUBJECT COMPLETION AND WITHDRAWAL

A subject is considered to have completed the study if he/she has had an initial study procedure and has follow-up information through 12 months.

Subjects will be informed that they have the right to withdraw from the study at any time for any reason, without prejudice to their medical care. The investigator also has the right to withdraw subjects from the

study for any reason. If a subject has a kidney transplant and/or current dialysis access is abandoned, he/she will be withdrawn from the study. If a subject is withdrawn from the study, the reason will be recorded on the end of study form. If a subject signs informed consent and is not enrolled in the study for any reason, the subject is a screen failure. A record of all subjects who signed an informed consent will be maintained.

Subjects will be considered lost to follow up if:

- The site has documented attempts to contact the subject at least three times without success, AND
- The site has a documented attempt to contact the subjects' dialysis center, AND
- The site has a documented attempt to contact the subjects' managing physicians

Subjects who are withdrawn from the study after completion of the study procedure for any reason will not be replaced. All subjects regardless of whether or not they complete the study, will be included in the Intent-to-Treat (ITT) population. The Sponsor may terminate the study at any time. In addition, termination or modification may be recommended for any other perceived safety concern based on clinical judgment of the Data Monitoring Committee (DMC) members.

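### Section 9 assigns no analysis set to 30-day patency; its only efficacy set is per-protocol in content, and the ITT population promised in Section 6 is never defined or used

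*Combined protocol and SAP*

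**What the plan says.** Section 9 (Analysis Sets) lists two populations.

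- Safety: "The safety population will include all enrolled subjects who received the treatment".
- Efficacy: "The efficacy population will include all enrolled subjects who received the treatment as specified in the protocol and met all eligibility criteria".

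Section 6 refers to a third: "All subjects regardless of whether or not they complete the study, will be included in the Intent-to-Treat (ITT) population". ITT appears nowhere else in the supplied text.

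No sentence in Section 9 ties a set to an endpoint. The 30-day patency result "will be summarized using number and proportion of subjects with Target Lesion Primary Patency at that timepoint", with no denominator named, and the primary safety summary is worded the same way. Section 9 describes the study as observational, plans no comparisons, and promises confidence intervals where possible without giving a level or method.

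**The concern.** The Efficacy Population adds two filters to the Safety Population: treatment must have been delivered the way the protocol prescribes, and every entry criterion must have been satisfied. Those are per-protocol conditions under another name. Since it is the only efficacy set that Section 9 defines, an analyst would most naturally use it for 30-day patency.

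In a single-arm study the main result is one proportion with its interval, so the choice of denominator matters directly. A placement that departed from instructions may be related to early failure. If such subjects are removed, the reported patency describes a selected group rather than everyone in whom the device was tried. Section 12 has deviations recorded on a form, but Section 9 does not say which deviations or eligibility breaches remove a subject, or when that is decided.

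**Working it through.** **1. The sets side by side**

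| Set | Where | Enrolled | Received treatment | Treated per protocol | All criteria met | Linked to an endpoint |
|---|---|---|---|---|---|---|
| ITT | Section 6 | all subjects | not required | not required | not required | no |
| Safety | Section 9 | yes | yes | not required | not required | no |
| Efficacy | Section 9 | yes | yes | yes | yes | only by its name |

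**2. Which gap matters**

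Inclusion criterion 7 requires full balloon expansion at the target lesion before enrollment. Appendix A puts enrollment and stent graft placement at the same visit, Visit 1. Section 6 classes anyone who consents but is not enrolled as a screen failure. There is therefore little room for an enrolled subject without an implant, and the ITT and Safety sets probably nearly coincide. The gap that matters is between those two and the Efficacy Population.

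**3. Possible size (illustration only)**

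The plan offers no figure to reproduce here. It gives approximately 50 subjects but no assumed patency, precision target, or rate of failed placement or later-found ineligibility. Inputs:

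- 50 subjects, from Section 9.
- 5 patency losses by day 30, assumed. The all-treated result is then 45/50 = 90.0%.
- k subjects left out, of whom j are losses, assumed.
- Exact (Clopper-Pearson) two-sided 95% intervals; level and method assumed.

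Leaving out k subjects removes k − j patent ones, so

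efficacy proportion = (45 − (k − j)) / (50 − k).

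| k | None of those left out is a loss (j = 0) | All are losses (j = k) | Shift from 90.0%, in points |
|---|---|---|---|
| 1 | 44/49 = 89.8% | 45/49 = 91.8% | −0.2 to +1.8 |
| 2 | 43/48 = 89.6% | 45/48 = 93.8% | −0.4 to +3.8 |
| 3 | 42/47 = 89.4% | 45/47 = 95.7% | −0.6 to +5.7 |

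Intervals: 45/50, 78.2 to 96.7; 42/47, 76.9 to 96.5; 45/47, 85.5 to 99.5.

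With 3 losses instead of 5, the all-treated result is 47/50 = 94.0% (83.5 to 98.7). Leaving out 2 to 5 subjects then gives between 42/45 = 93.3% (81.7 to 98.6; five left out, none a loss) and 100%, for example 47/47 (92.5 to 100; three left out, all losses).

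When patency is high, the largest possible upward shift exceeds the largest downward one. That is a statement about bounds and does not predict the actual shift.

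**The case against.** **The text does not commit patency to the Efficacy Population.** Section 9 speaks of subjects without qualification, and Section 6 puts everyone in an ITT population, so an ITT denominator is also open. This stands. The established defect is an unassigned denominator; the selection problem is conditional on the most natural reading. It does not remove the need for the edit, because otherwise the primary denominator remains undefined.

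**Treatment per protocol may be defined elsewhere.** Section 5 refers delivery of the stent graft to Appendix B, whose content is redacted. It may say what counts as conforming treatment or as treatment received. This stands as a reservation.

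**The largest shifts need every excluded subject to be a loss.** This is correct. Under the patency definition in Section 2.1, a failed placement whose lesion stays open after angioplasty alone still counts as patent. The upper ends of the ranges are bounds.

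**Stronger readings that the documents do not support:**

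- A reader might infer that an early access loss could later be turned into ineligibility, because criterion 18 excludes subjects whose "access is anticipated to be abandoned within 3 months" and criterion 22 covers "Any other condition deemed exclusionary in the opinion of the investigator". Both are judgements made at Visit 1, and no retrospective eligibility review is described. Abandonment of the access is also not a target lesion patency event.
- A reader might infer from "A formal interim analysis will be completed when all subjects complete the 6-month visit" and "As the interim analysis will be the primary effectiveness analysis" that exclusions will be decided with outcomes in hand. The documents do not say so. Any 30-day analysis follows 30-day results, and in an open single-arm study sites see outcomes as they occur. What remains is that no time is fixed for deciding membership.
- A reader might think that the Efficacy Population drops subjects with incomplete follow-up. Its definition does not.

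**Conclusion.** The point holds as a mismatch between Sections 6 and 9 and an unassigned denominator for both primary endpoints; the text settles that much. That 30-day patency would be estimated in a selected set is conditional on the Efficacy Population being used for it, which its name implies but no sentence states.

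The size and direction of any bias are unknown. In the main illustration, leaving out 3 of 50 subjects moves 90.0% by between −0.6 and +5.7 points. The number of losses, the number excluded, the 95% level and the exact method are all assumptions.

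No test, error rate or power statement is affected, since none is planned. This is an inexpensive improvement to the plan and does not undermine the study.

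**What to change.** In Section 9:

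1. Name the set for each primary endpoint. For 30-day patency, use all enrolled subjects in whom stent graft delivery was attempted, regardless of technical success or later-found ineligibility.
2. Align the ITT sentence in Section 6 with this set. Because the set is slightly narrower than all subjects, list any enrolled subject without an attempt, with the reason.
3. Keep the present Efficacy Population as a supportive analysis. Fix in advance which deviations and eligibility breaches exclude a subject, judge them on Visit 1 information (subject to whatever Appendix B says), and report the number and reasons.
4. Optionally, add a sensitivity analysis that counts failed placements as loss of patency at day 0. The existing patency definition stays in the primary analysis.

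The cost is wording in two sections, a short list of excluding deviations, one extra table, and 30-day data on any failed attempt. Technical success, deviations and procedure-day adverse events are already recorded, so the subjects concerned can be identified. The headline proportion may change slightly.

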2 STUDY OBJECTIVES

2.1 Primary Objectives

Safety

- Proportion of subjects without any localized or systemic safety events through 30 days that affect the access or venous outflow circuit and resulted in surgery, hospitalization, or death
 - Safety events in this calculation will not include venous outflow obstructions, which are captured in the calculation of Assisted Primary Patency of the target lesion, Assisted Primary Patency of the venous outflow circuit and Index of Patency Function

Effectiveness

- Proportion of subjects with Target Lesion Primary Patency at 30 days
 - Time to loss of Target Lesion Primary Patency is defined as the time interval of uninterrupted patency from initial study procedure to the next intervention performed on the target lesion or uncorrectable target lesion occlusion, whichever occurs first

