2.2 Secondary Objectives

- Proportion of subjects with Target Lesion Primary Patency at 3, 6 and 12 months
- Proportion of subjects with Assisted Primary Patency of the target lesion at 30 days, 3, 6 and 12 months
 - Time to loss of Assisted Primary Patency of the target lesion is defined as time following study procedure until uncorrectable target lesion occlusion
- Proportion of subjects with Primary Patency of the venous outflow circuit at 30 days, 3, 6, and 12months
 - Time to loss of Primary Patency of the venous outflow circuit is defined as the time following initial study procedure until the next venous outflow circuit intervention
- Proportion of subjects with Assisted Primary Patency of the venous outflow circuit at 30 days, 3, 6 and 12 months.

- Time to loss of Assisted Primary Patency of the venous outflow circuit is defined as the time following initial study procedure until complete access abandonment.
- Index of Patency Function at 3, 6 and 12 months, defined as time from initial study procedure to complete access abandonment divided by number of venous outflow circuit re-interventions to maintain hemodialysis
- Procedure or device related adverse events at 3, 6 and 12 months
- Clinical Success
 - The resumption of successful dialysis through existing access for at least one session following initial study procedure
- Anatomic Success
 - Less than 30% residual stenosis immediately following study procedure
- Procedural Success
 - The achievement of both clinical and anatomic success

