12 PROTOCOL COMPLIANCE

The Investigators will conduct the trial in compliance with the protocol provided by Merit Medical Systems. Modifications to the protocol must not be made without agreement of the Investigator and Merit Medical Systems. Changes to the protocol potentially affecting safety or efficacy will require written EC approval/favorable opinion prior to implementation, except when the modification is needed to eliminate an immediate hazard(s) to subjects. Any deviations from the protocol must be captured on the electronic protocol deviation form and reported to EC and any other regulatory authorities as applicable.

DCO20-036_09OCT2020

Confidential

Page 25 of 34

Effort should be made to have subjects return to study physician office for in-person follow-up visits, but if subjects are unable or unwilling to complete visits the clinical trial site may obtain subject status information from the subject's dialysis center or other treating physician. The clinical trial site will confirm with subjects' dialysis centers whether any access or venous outflow dysfunction revisions have happened at other facilities.

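### Patency at 3, 6 and 12 months is planned as a crude proportion of a time-to-loss endpoint, with no rule for subjects who leave while patent

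*Combined protocol and SAP*

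**What the plan says.** Section 9 of the combined protocol and SAP states that 30-day target-lesion primary patency "will be summarized using number and proportion of subjects with Target Lesion Primary Patency at that timepoint". It then extends this to the later time points: "This methodology will be repeated to test secondary endpoints, proportion of subjects with: target lesion Primary Patency at 3, 6, and 12 months". The same sentence covers Assisted Primary Patency of the target lesion and both patency measures of the venous outflow circuit. Confidence intervals are promised wherever possible, with no method named.

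The endpoints themselves are durations. Section 2.1 measures target-lesion primary patency "from initial study procedure to the next intervention performed on the target lesion or uncorrectable target lesion occlusion, whichever occurs first". Section 2.2 gives a time to loss for each of the other three; for circuit Assisted Primary Patency it is "defined as the time following initial study procedure until complete access abandonment".

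On early exit, Section 6 says: "If a subject has a kidney transplant and/or current dialysis access is abandoned, he/she will be withdrawn from the study". It adds: "Subjects who are withdrawn from the study after completion of the study procedure for any reason will not be replaced". The nearest thing to a rule for leavers is also there: "All subjects regardless of whether or not they complete the study, will be included in the Intent-to-Treat (ITT) population". Section 9 does not list that population among its analysis sets; it defines a Safety Population and an Efficacy Population. Under Section 12, when a visit is not possible, "the clinical trial site may obtain subject status information from" the dialysis center or another treating physician.

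**The concern.** A crude 12-month proportion needs a 12-month status for every subject in the denominator. A subject who dies, is transplanted, or is lost with the lesion still patent has none. The analyst must remove that subject, count the subject as patent, or count the subject as a failure. The plan does not choose, and it mentions neither censoring nor imputation nor a denominator rule. The choice could therefore be made after the data are seen, and the promised confidence interval would belong to a quantity that was not fixed in advance.

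Abandonment needs its own line. For circuit Assisted Primary Patency it is the only loss event and also a reason for withdrawal, so the plan should say plainly that it counts as the event. For the other three endpoints it is an exit that may be related to loss of patency.

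The stakes are limited: these are descriptive secondary endpoints with no comparison and no threshold. They are, however, the study's only patency figures beyond 30 days for a first-in-human device.

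**Working it through.** The plan gives no expected patency, leaving rate or precision target, so there is no figure of its own to reproduce. The check asks how far the 12-month figure depends on the missing rule.

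**Inputs**
- Number of subjects: about 50 (Section 9).
- True 12-month target-lesion primary patency S: 47.6% (stent-graft arm of the randomized AV-graft trial in Section 1.2) or 67% (central-vein stent-graft series of 42 subjects in Section 1.3). Applying either to this device is an assumption.
- Proportion leaving per year d: 10% to 25%, an assumption. Section 1.1 cites 20% to 25% one-year mortality on hemodialysis, but that is background mortality. Section 3.2 excludes subjects with life expectancy of 12 months or less, which should lower it.
- Leaving is independent of patency loss, and both hazards are constant (assumptions).

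**Formulas, at one year**
- Loss hazard λ = −ln(S); leaving hazard μ = −ln(1−d).
- Still followed and patent: F = S(1−d).
- Loss seen before leaving: O = λ/(λ+μ) × (1−F).
- Left while patent: 1 − F − O.
- Remove only patent leavers, keeping earlier losses as failures: F/(F+O).
- Count patent leavers as patent: 1 − O.
- Count patent leavers as failures: F.
- Exclude every leaver whatever their status: S(1−d)/(1−d) = S.

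**One case in full** (S = 47.6%, d = 25%): λ = 0.742, μ = 0.288, F = 0.357, O = 0.742/1.030 × 0.643 = 0.463, left while patent = 0.180. Removing patent leavers gives 0.357/0.820 = 43.5%. Counting them as patent gives 53.7%. Counting them as failures gives 35.7%.

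**12-month shifts from S, in points**

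| S | d | Patent leavers removed | Counted as patent | Counted as failures |
|---|---|---|---|---|
| 47.6% | 10% | −1.5 | +2.3 | −4.8 |
| 47.6% | 25% | −4.1 | +6.1 | −11.9 |
| 67% | 10% | −1.3 | +1.6 | −6.7 |
| 67% | 25% | −3.6 | +4.0 | −16.8 |

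The share leaving while patent runs from 7.1% to 20.8%, or about 4 to 10 of 50 subjects. Excluding every leaver has no bias under independence, but it discards losses already observed and leaves about 50 × 0.90 = 45 down to 50 × 0.75 = 37.5 subjects.

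**Sensitivity to the hazard shape.** With hazards fitted piecewise to the cited 97/81/67% curve (3, 6, 12 months), the shifts are −1.2 to −3.3 (removed) and +1.7 to +4.4 (as patent). For assisted patency, the cited 100/100/80% curve gives −0.4 to −1.2 and +1.5 to +3.8.

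**Earlier time points** (constant hazards). At 6 months: −0.4 to −1.7 and +0.5 to +2.0. At 3 months both are within 0.6. At 30 days both are within 0.1, and counting patent leavers as failures lowers the figure by 0.8 to 2.3.

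**Against sampling error.** An exact 95% interval (method assumed) is about 26 to 29 points wide at 50 subjects for rates in this range, and up to about 32 points wide with 40 remaining.

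**The case against.** The strongest reply is that a literal count over all treated subjects is a coherent summary. Section 2.1 counts only an intervention on the target lesion or an uncorrectable occlusion as a loss, so a subject who dies with a patent lesion has not had one. Counting such subjects as patent gives one minus the cumulative incidence of loss, with leaving as a competing event. This stands: the 1.6 to 6.1 points are the gap between two estimands, and the protocol does not name patency had nobody left as its target. What remains is that the plan does not say which it intends.

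A reader might infer that any exclusion of leavers biases the result downward. That is not so. Under independence the understatement arises only when patent leavers are removed while earlier losses are kept.

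A reader might also infer that circuit Assisted Primary Patency is bound to come out at 100%, because everyone who abandons the access is withdrawn. The documents do not support that. Section 2.2 makes abandonment the loss event, Section 6 keeps non-completers in the ITT population, and the Efficacy Population in Section 9 has no completion requirement. All three weigh against a completers-only denominator.

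Section 12 does reduce missing status from missed visits. It cannot supply a 12-month status after death, or say how a transplant counts. Finally, Section 4 calls follow-up to 12 months supplementary, which argues for a low severity but does not supply the rule.

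**Conclusion.** The gap is real and minor. The plan summarises time-to-loss endpoints as crude proportions and assigns no outcome to subjects who leave while patent. Confidence in that reading of the text is high.

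Confidence in the size is moderate, because the patency and leaving rates are borrowed or assumed and leaving is taken as independent of loss. Removing only patent leavers understates 12-month target-lesion primary patency by 1.3 to 4.1 points. Counting them as patent answers a different question and reads 1.6 to 6.1 points higher. Counting them as failures reads 4.8 to 16.8 points lower and conflicts with the loss definition in Section 2.1. The first two shifts are well inside the sampling error at 50 subjects.

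It would go too far to say that the study's conclusions are undermined: the 30-day primary endpoint is little affected, and no comparison depends on the later rates.

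**What to change.** In Section 9:
- Estimate the 3-, 6- and 12-month patency endpoints by Kaplan-Meier with 95% confidence intervals (for example log-log with Greenwood variance), using event dates. Censor patent subjects at death, transplant, withdrawal or last known status.
- For circuit Assisted Primary Patency, state that abandonment is the event. For the other three endpoints, censor at abandonment if the defined loss has not already occurred, and add a sensitivity analysis counting abandonment as a loss.
- Report a cumulative-incidence analysis with death and transplant as competing events, labelled as a different estimand.
- Keep the crude counts, with the number of leavers by reason at each time point.

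The cost is some SAP wording and a little more analysis work. The time-to-loss definitions and the Index of Patency Function already need event dates, so no new data should be required; the case report form is not in the documents, so this should be checked.

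There are two downsides. Kaplan-Meier relies on independent censoring. The abandonment sensitivity analysis shows part of that dependence: it shifts the 12-month figure by S × a, where a is the assumed yearly abandonment. That is 2.4 to 3.4 points at a = 5% and 4.8 to 6.7 at a = 10%. The interval is also slightly wider than if nobody left: 26.7 to 29.1 points against 26.2 to 27.1 in simulations with 50 subjects under the same assumptions.
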